Chronic knee OA pain is influenced by systemic inflammation and metabolic factors such as poor diet, excess weight, and metabolic syndrome, which contribute to “meta-inflammation” through dysregulation of adipokines, cytokines, and lipids (Zhang et al. 2024 PMID: 38243159). A systematic review and meta-analysis of 73 studies show significant reductions in self-reported pain severity following nutrition interventions (Brain, K. et al. 2019 PMID: 30294938) and prebiotics may hold promise for the management of knee OA in adults with obesity (Fortuna, R. et al. 2024 PMID: 38713231). In addition, the endocannabinoid (EC) system plays a central role in pain regulation and emotional response to chronic pain (Woodhams, S. G., et al. 2015). PMID: 25846617). Prebiotic fibre supplementation may support gut health, reduce systemic inflammation, and improve biomarkers linked to OA and chronic pain, complementing the effects of exercise.

Emerging evidence links gut microbiome composition to OA-related knee pain, with studies indicating its role in pain intensity, progression, and sensitivity- including neuropathic pain - largely through inflammation modulation (Ding, W. et al. 2021 PMID: 32889847). Short chain fatty acids (SCFAs), produced by bacterial fermentation of dietary fibre, mediate many of the microbiome’s anti-inflammatory effects. However, the interactions between physiotherapy exercise, prebiotic

inulin supplementation, pain modulation, inflammatory biomarkers, and the gut microbiome remain poorly understood. Specifically, the effects of inulin and exercise on pain, microbiome composition, inflammatory markers, and circulating SCFA levels in individuals with knee OA have yet to be explored.

Rationale: This trial will adopt a 2x2 factorial design to assess the individual and combined effects of exercise and prebiotic inulin supplementation over six weeks. The study will evaluate their effect on knee osteoarthritis (OA) pain, as well as molecular and gut microbiome parameters.

STUDY OBJECTIVES

PRIMARY OBJECTIVE

1-To assess the magnitude of the effect of prebiotic supplementation (inulin) side by side with physiotherapy exercise versus placebo (maltodextrin) on knee pain

SECONDARY OBJECTIVES

1-To assess the combined effects of exercise and prebiotic inulin supplementation (synergistic effect) over six weeks

- Are currently following or anticipated to commence a specialised commercially available weight loss diet and/or programme
- Pregnant or breastfeeding
- History or current psychiatric illness (including clinical depression)
- History or current neurological condition (e.g. epilepsy)
- Those undergoing revision, having severe hip OA, inflammatory arthropathies
- Diagnosed non-OA cause of knee pain (e.g. rheumatoid arthritis)
- Neuropathy or diabetes mellitus
- Having taken part in a research study in the last 3 months involving invasive procedures or an inconvenience allowance

RANDOMISATION AND BLINDING

Randomisation will be done using a computer-generated randomisation and allocation concealment software called “sealed envelope” (<https://www.sealedenvelope.com/>). At least thirty participants will be divided equally between the treatment arms. Blinding for the exercise intervention is not feasible at this stage since participants will be informed if they have been randomly assigned to one of the exercise groups. Because this might affect the motivation of

participants who were randomly assigned to the non-exercise arms, they will be offered access to the web-based exercise programme after completing the trial. Although it is challenging to blind exercise intervention studies, both the research examiner and the participants will be blind to the intervention and the food supplementation.

MATERIALS

Inulin fibre (20g) in powder form, maltodextrin (10g) in powder form, Joint Academy app, faecal sample kit, blood sample collection materials.

PHYSIOTHERAPY INTERVENTION

INSPIRE will use a web-based exercises platform known as Joint Academy (JA) as a previous RCT from our group demonstrated promising results for this platform (Gohir et al 2021 PMID: 33620447). The Swedish face-to-face self-management programme "Artrosskolan" (The Osteoarthritis School), which offered structured information and exercises for knee arthritis to a relevant population with the condition, served as the model for this programme. The JA company has granted permission for this study to be carried out using their digital platform.

The exercise intervention has been described in detail previously (Gohir et al 2021 PMID: 33620447). It is focused on a mixture of concentric and eccentric exercises with open and closed-chain movements, for strengthening the legs including the muscles around the hips and knee joints as well as exercises to improve balance. An open kinetic chain is defined as "a combination of successively arranged joints in which the terminal segments can move freely" (Karandikar et al 2011 PMID: 21871418), while closed chain exercises are those in which the proximal joints move while the distal portion of the extremities is in a stationary position (Karandikar et al 2011 PMID: 21871418). The programme also includes educational sessions covering the fundamentals of OA, its treatment, self-managing symptoms of OA and the benefits of maintaining a healthy lifestyle.

DIETARY INTERVENTION

Inulin fibre (20g) in powder form (commonly found in root vegetables such as chicory) will be randomly allocated to eligible participants in order to test specific effects on gut microbiome

composition and metabolic markers. Inulin is easily dissolvable in liquid and can be incorporated into the usual diet - by adding water, juice, smoothies, cereal, yogurt.

CONTROL PLACEBO GROUP

The control group will continue with routine self-management which is offered in the community setting and will be instructed to receive maltodextrin (10g) in powder form (commonly found in corn, potatoes, rice) which can be consumed by adding to breakfast cereal/ smoothie/ yogurt or drink of choice similar to inulin will serve as a control/placebo to compare the effects observed with inulin.

FOLLOW UP DURATION

Six weeks post-intervention.

RESEARCH ASSESSMENT

Following outcome measures will be assessed:

- Quantitative Sensory Testing – QST (Pressure pain threshold – PPT and Temporal summation – TS)
- SCFAs, EC, gut microbiome and inflammatory pain-related biomarkers
- Physical functioning (Time up and go test, 30-second sit to stand test)
- Grip strength
- Hospital Anxiety and Depression Scale (HADS)

DESCRIPTION OF INTERVENTION

The study will be communicated verbally and in writing to participants who have knee pain from OA. Participants who meet the study's eligibility requirements will sign an informed consent form and be randomly assigned to either the interventional groups or the control/placebo group.

All groups will have an assessment session with experienced staff with blood samples taken at baseline and a Numerical Rating Scale (NRS) (Hjermstad, M. J. et al. 2011 PMID: 21621130), physical functioning and other outcomes (grip strength (Roberts, H. C. et al. 2011 PMID: 21624928), Time up and go test (Barry et al 2014 PMID: 24484314), 30-second sit to stand test (Jones, C. J., et al. 1999 PMID: 10380242), Quantitative Sensory Testing (QST) (Arant, K. R. et al. 2022 PMID: 34597800)). Participants will be asked to fill in questionnaires on health and anxiety/depression (Hospital Anxiety and Depression Scale (HADS) (Zigmond, A. S. & Snaith, R. P. 1983 PMID: 6880820) that they will have been sent via post before the study visit. They will also be sent a faecal sample kit and will be asked to provide a faecal sample to bring to their baseline appointment.

The exercise interventional groups will be sent an email with a link to access the JA online platform. The physiotherapy intervention will begin once log-in and a kick-off call with an assigned personal physiotherapist is complete. The intervention will consist of a 6-week online physical therapy course that includes exercises, information, contact with a personal physiotherapist, and instruction on behavioural and lifestyle modifications, and can be accessed using a smartphone or tablet. Through frequent email prompts, the programme also promotes commitment to physical activity. Participants will first complete a physical test measuring lower limb strength and respond to an online questionnaire that covers topics like physical function, health-related quality of life, and the severity of joint discomfort. The online baseline evaluation will include this questionnaire. In addition to some functional exercises like sit-to-stand and stair climbing, the exercise intervention will include knee and hip exercises.

The placebo and inulin groups will receive pre-measured pots containing either the supplement or placebo powder for each week, along with scoops. Participants will be instructed to take either 2 or 3 scoops daily, depending on whether they are in the inulin or placebo group. They will also be provided with guidance on incorporating their daily dose into their diet, such as mixing it into smoothies or using it as a topping on yoghurts and breakfast cereals. Participants will be asked to maintain a daily dietary compliance record to track their supplement intake, including any missed doses and the reasons for not taking the supplement. If participants experience adverse effects, such as severe bloating or nausea, that prevent them from continuing with the supplement, they will be instructed to notify a member of the study team.

After the six weeks of interventions, all participants will fill in the same questionnaires and perform the physical tests, to enable evaluation. Participants and the researcher will meet in person twice: once at enrolment and again six weeks later.

OUTCOMES

Primary outcome:

- Numerical Rate Score (NRS) for pain to assess changes in response to the interventions.

Secondary outcomes:

- Changes in markers of pain assessed by quantitative sensory testing, and in markers of inflammation
- Changes in gut microbiome composition and serum levels of short chain fatty acids (SCFAs) in response to the interventions.
- Changes in functional outcomes (e.g., 30 second sit to stand test, get up and go test)

STATISTICAL ANALYSIS PLAN

The clinical trial data will be analysed using the appropriate parametric and non-parametric statistical tests, we will compare outcome measures (such as pain sensitivity and pain ratings) between the exercise and non-exercise groups while adjusting for baseline scores.

Secondary analyses (i.e., correlations between changes in SCFAs and changes in pain measures) will be conducted using the appropriate type of statistical test based on data normality (e.g., Spearman's).

A planned analysis of covariance (ANCOVA) will be conducted to assess differences in follow-up outcome measures among treatment groups while adjusting for baseline levels. The model will include treatment group (arm: inulin only, exercise only, inulin & exercise, control/placebo) as a categorical independent variable and baseline outcome scores as a covariate. Model assumptions will be evaluated through residual diagnostics to ensure the validity of the analysis

To further explore differences between groups, post hoc pairwise comparisons will be conducted, including comparisons between groups and an evaluation of potential interactions to assess potential synergy between treatments.

R studio and Graph Pad PRISM will be used for the statistical analyses.

SAMPLE SIZE AND JUSTIFICATION

Primary outcome is a Numerical Rate Score (NRS) for pain as used in our previous exercise intervention study (Gohir et al 2021 PMID: 33620447). The 2x2 factorial design with 30 individuals per block (total n=120) has 80% to detect differences of 0.51 SDs. In our own study delivering the exercise intervention the effect size observed was a drop of 0.84 SDs in the exercise arm compared with only 0.2 SDs in the control arm (who only received a leaflet). In addition, the study has adequate power to detect moderate main effects of inulin on pain outcomes, with 30 participants per group providing ~75–80% power to detect an effect size of Cohen's $d \sim 0.6$ at $\alpha = 0.05$. If changes in gut microbiome via dietary supplementation can achieve a difference of 0.51 or higher in NRS, the study is powered to detect them.

Secondary outcomes: a key goal of this study is to link changes in molecular markers in serum to changes in pain and other outcomes (n=120, 60 per arm for the 2x2 intervention). For instance, the effect sizes in changes in a circulating molecular pain modulator observed previously from 0.32 to 0.71 nmol/L; SD=0.61 after 6 weeks of inulin supplementation hence yielding an effect size of 0.62 STDs. It increased from 1.61-1.82 nmol/L; SD=0.31 yielding an effect size of 0.61 STDs with the exercise intervention.

DATA MANAGEMENT

Data will be gathered during the first and last sessions of the INSPIRE trial. Trained local research personnel will compile all the data sources, and data entry in a RedCAP database will be done in a consistent manner. This will comprise data from QST, 30CST, and TUG as well as questionnaires. The data entry site will enter data from the clinical research forms (CRF) from the initial and final study visits.

ADVERSE EVENTS

Since the interventions in the current study are using components sourced from common foods and routine exercise, we foresee no adverse reaction or side effects. Increasing fibre intake may result in bloating amongst those who have a low habitual intake of dietary fibre. However, such effects are mild and not considered as a safety concern. Participants will be asked to record any side effects like bloating using the dietary compliance diary and will be advised to stop taking the supplement if they experience severe bloating. Between 2008 and 2017, 75,000 participants participated in these activities' trials, and no significant side effects were reported (Thorstensson, C. A. 2015 PMID: 25345913). An increase in back, hip, or knee pain is a remote possibility (Luan, L., 2022 PMID: 35091326). Using an online interface, we will track the patient's pain levels every week to see if there has been an increase in discomfort. The subject will be advised to discontinue

study participation and get in touch with their GP if their pain worsens to the point that they begin to struggle with everyday tasks.

Criteria for terminating the study: It is not anticipated that circumstances will arise that necessitate the termination of this study because it only consists of two assessments, does not involve investigational medications or medical devices, and the same intervention has not resulted in any serious adverse events in over 70,000 participants in Sweden.

Funding source

This study is funded by UKRI grant MR/W026813/1 and supported by infrastructure provided by the NIHR Nottingham Biomedical Research Centre (BRC).

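### The SCFA–pain change correlations name no arm term; if the four arms are pooled, they mix treatment effects with the association among people treated alike

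*Combined protocol and SAP*

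**What the plan says.** The STATISTICAL ANALYSIS PLAN section gives the secondary analyses one sentence. They are "correlations between changes in SCFAs and changes in pain measures", given as the instance of a wider class, and they "will be conducted using the appropriate type of statistical test based on data normality", with Spearman as the example. No arm term, stratification, partial correlation or pooling rule is given.

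An arm term appears later in the same section, for the ANCOVA of follow-up outcomes adjusted for baseline: "The model will include treatment group (arm: inulin only, exercise only, inulin & exercise, control/placebo) as a categorical independent variable". Nothing extends it to the correlations.

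SAMPLE SIZE AND JUSTIFICATION presents it as a main aim to "link changes in molecular markers in serum to changes in pain and other outcomes (n=120, 60 per arm for the 2x2 intervention"). The second secondary objective, on the molecular pathways of pain relief, depends on the same analysis. The background text describes "Short chain fatty acids (SCFAs), produced by bacterial fermentation of dietary fibre", as carriers of many of the microbiome's anti-inflammatory effects. Inulin is a dietary fibre, so the plan's own reasoning has it raising SCFAs and, through them, easing pain.

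**The concern.** A correlation of changes across all 120 participants has two sources. One is the association among people given the same treatment. The other is the spread of arm means: if inulin raises SCFAs and lowers pain, the inulin arms sit apart from the rest on both axes, and that alone produces a negative correlation. The second part restates treatment effects that the ANCOVAs already estimate. A pooled coefficient cannot separate two unrelated effects of inulin from a marker that goes with pain relief.

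At stake is how the pathway objective is read. A pooled correlation could be reported as marker–pain evidence when it partly repeats the trial's treatment effects. A real within-arm link could also be inflated or diluted, depending on its sign. Because the plan does not say which association is meant, the choice could be made after the data are seen.

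**Working it through.** **Inputs from SAMPLE SIZE AND JUSTIFICATION**
- 30 per arm, 120 in total; alpha 0.05, taken as two-sided.
- Inulin on the marker: 0.62 SD, from "after 6 weeks of inulin supplementation hence yielding an effect size of 0.62 STDs". This is a before–after change in another circulating marker, used as a stand-in. The means and SD printed there give (0.71 − 0.32)/0.61 = 0.64; I keep the stated 0.62.
- Inulin on pain: 0.51 SD, from "If changes in gut microbiome via dietary supplementation can achieve a difference of 0.51 or higher in NRS", read in SD units as in the preceding power statement. It is a detectable difference, not an expected effect.
- Exercise on pain: from "the effect size observed was a drop of 0.84 SDs in the exercise arm compared with only 0.2 SDs in the control arm", 0.84 − 0.20 = 0.64 SD.
- Exercise on the marker: 0, or the stated 0.61 SD as a variant.

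**Assumed, not in the documents:** any SCFA effect, the SD of change (set to 1), and the within-arm correlation ρ (0, +0.25 or −0.25).

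**The plan's own figure.** It gives no power for the correlations. Its 80% for 0.51 SD reproduces at 60 v 60: 0.51 × √(60/2) = 2.79; 2.79 − 1.96 = 0.83; power 79.8%.

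**Expected pooled correlation.** With equal arms, additive effects a (marker) and b (pain), and subscripts I (inulin) and E (exercise):

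r = [ρ + ¼(a_I·b_I + a_E·b_E)] / √{[1 + ¼(a_I² + a_E²)] · [1 + ¼(b_I² + b_E²)]}

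With a_I = 0.62, b_I = −0.51 and no exercise effects, the between-arm term is ¼ × 0.62 × (−0.51) = −0.079 and the denominator is √(1.096 × 1.065) = 1.080.
- ρ = 0: r = −0.079/1.080 = −0.07
- ρ = +0.25: r = 0.171/1.080 = 0.16
- ρ = −0.25: r = −0.329/1.080 = −0.30

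If exercise also moves both (0.61 and −0.64), the between-arm term is −0.079 − 0.098 = −0.177, the denominator is √(1.189 × 1.167) = 1.178, and ρ = 0 gives r = −0.15.

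**Share of trials with a significant result.** Simulation, normal changes, 20,000 trials per main case (two standard errors at most 0.7 points). Pooled Spearman (118 df) is compared with partial Spearman given inulin, exercise and their product (115 df). Ranges cover an exercise effect on pain of 0 or 0.64 SD.

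| Case | Pooled | Arm-adjusted |
|---|---|---|
| ρ = 0, inulin 0.62 / 0.51 | 11–12% | 5% |
| ρ = 0, exercise also moves both | about 36% | 5% |
| ρ = 0, marker effect 0.3 SD or inulin pain effect 0.25 SD | 6–7% | 5% |
| ρ = 0, no treatment moves both | 5% | 5% |
| ρ = +0.25 (opposes treatment effects) | 34–37% | 73–74% |
| ρ = +0.25, smaller or no inulin effects | 51–66% | 73–75% |
| ρ = +0.25, exercise also moves both | about 8% | 72–73% |
| ρ = −0.25 (same sign as treatment effects) | 88–91% | 73–74% |

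Pearson gives the same picture: 38–40% pooled v 78% adjusted in the main opposite-sign case.

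**Analysis by factor level** (n=60, one exercise level, ρ = 0). Inulin still varies inside the level. The unadjusted correlation is significant in about 8%, 14% and 21% of trials for marker effects of 0.62, 1.0 and 1.5 SD, against 5% adjusted.

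**The case against.** **Pooling is inferred.** This stands. The correlation sentence is silent, and the n=120 is followed by a count per arm of 60. A reader might infer that the plan commits to a wrong pooled analysis; the text does not support that. What is established is that the analysis is unspecified. Reading the 60 as analysis by factor level reduces the mixing but does not fully remove it.

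**The opposite-sign case is the one the protocol least expects.** This stands too. A reader might take the 34–37% v 73–74% contrast as the main result and conclude that pooling hides the link. The rationale points to the same sign, where pooling gives more significant results and a modestly inflated coefficient (about −0.30 for a true −0.25). Even in the main opposite-sign case the link is diluted, not reversed: a significant result in the wrong direction occurs in under 1% of trials.

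**The pooled correlation is a genuine quantity.** Agreed. A reader might call the 11–12% an inflated Type I error. It is not, because the overall association is truly non-zero; the error would lie in reading it as a link among people treated alike. Arm adjustment also discards randomised, treatment-induced variation, and what remains is observational. This is a good reason to report both figures, and not a reason to leave the choice open.

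**The misleading-positive risk is modest at the central inputs.** True: |r| is about 0.07, and the excess nearly vanishes with smaller effects. It grows if exercise moves both variables, and SAMPLE SIZE AND JUSTIFICATION does report a serum marker rising with exercise.

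**Conclusion.** The concern holds as a gap in specification. The plan does not say whether the SCFA–pain correlations are pooled or account for arm, and the two answer different questions. If they are pooled, the result mixes treatment effects with within-arm association, and the distortion can go either way. The sizes rest on a stand-in marker effect, a detectable rather than expected pain effect, unit SD of change and an invented within-arm correlation of 0.25, so they are illustrations and not forecasts. The direction does not depend on those values: mixing arises whenever a treatment moves both marker and pain, and disappears when none does.

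The point bears on the secondary pathway objective only. It is worth correcting because the correction is cheap, but it does not touch the primary analysis. The documents do not support a claim that the planned analysis is invalid, or that adjustment would establish mediation.

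**What to change.** Add to the STATISTICAL ANALYSIS PLAN, in substance:

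> The marker–pain analysis will report a partial Spearman correlation of change in marker with change in pain given the four-level arm (inulin, exercise and their product). The unadjusted pooled correlation will be shown beside it, labelled as including treatment effects. Neither will be taken as proof of mediation.

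A regression of pain change on marker change with both factors and their product is equally acceptable if named before analysis. Four separate within-arm correlations would also avoid the mixing, but each detects 0.25 in only about 24% of trials at n=30.

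**Cost.** Three sentences, no new data, and 3 degrees of freedom (118 to 115). With no treatment effects, power at a within-arm correlation of 0.25 falls by about 1 point (75% to 74%). When treatment and within-arm associations share a sign, the adjusted analysis gives about 5–18 points fewer significant results:
- 5, 10 and 18 points if inulin acts on pain only through the marker, with marker effects of 0.62, 1.0 and 1.5 SD. These become about 0.5, 7 and 15 points if exercise also lowers pain by 0.64 SD.
- 14–17 points at the 0.62 / 0.51 inputs.

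Part of that gap is treatment effect and not within-arm association, which is why the pooled figure should stay in the report.

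### The d ≈ 0.6 power sentence labels a 30-vs-30 cell comparison as the inulin main effect, and the SAP does not name the 60-vs-60 inulin margin that the 0.51-SD claim fits

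*Combined protocol and SAP*

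**What the plan says.** The SAMPLE SIZE AND JUSTIFICATION section makes two power statements about pain.

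- The first is for the whole design: "The 2x2 factorial design with 30 individuals per block (total n=120) has 80% to detect differences of 0.51 SDs". The same paragraph later applies this figure to the supplement: "via dietary supplementation can achieve a difference of 0.51 or higher in NRS, the study is powered to detect them".
- The second says that "the study has adequate power to detect moderate main effects of inulin on pain outcomes, with 30 participants per group", and gives the power as about 75–80% for Cohen's d of about 0.6 at alpha 0.05.

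The paragraph on secondary outcomes gives the size of a factorial margin: "n=120, 60 per arm for the 2x2 intervention".

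The STATISTICAL ANALYSIS PLAN section names these analyses:

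- a pooled comparison "between the exercise and non-exercise groups while adjusting for baseline scores";
- an ANCOVA, of which it says "The model will include treatment group (arm: inulin only, exercise only, inulin & exercise, control/placebo) as a categorical independent variable", with "baseline outcome scores as a covariate";
- follow-on work: "To further explore differences between groups, post hoc pairwise comparisons will be conducted, including comparisons between groups and an evaluation of potential interactions".

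It does not name a comparison of all inulin participants with all non-inulin participants. The PRIMARY OBJECTIVE sets inulin alongside exercise against placebo. That can be read as a main effect, as each active arm against placebo, or as the combination against placebo.

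**The concern.** In a 2x2 factorial trial, a main effect uses everyone: the two arms with inulin against the two without. With 30 per cell that is 60 against 60. The second power statement names a main effect but gives a group size of 30, which is the size of one cell. It also gives power no higher than the first statement for a larger effect, which cannot happen within one test.

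The SAP does not resolve this, because it pools over the other factor for exercise only. A reader cannot tell which test decides whether inulin reduces pain, or which power figure belongs to it. The choice among a margin and several cell pairs could then be made after the data are seen. A null inulin result would also be hard to interpret, because power at 0.51 SD depends heavily on which contrast was meant.

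**Working it through.** **Inputs from the documents.** 30 per cell, total 120, 1:1:1:1 allocation; 80% at 0.51 SD; about 75–80% at d of about 0.6 with 30 per group; alpha 0.05 (given with the second statement only).

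**Assumptions.** Alpha 0.05 two-sided for both statements, SD = 1, no dropout, no interaction, and 0.51 in NRS read as 0.51 SD. The documents give no baseline correlation, so the base case takes no gain from adjustment and a range follows.

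**Formula.** Noncentrality = d / √(2/n), with n per side. Approximate power = Φ(noncentrality − 1.960). The noncentral-t result is given after it.

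**1. Reproduce the 80% at 0.51 SD.** For 60 vs 60, √(2/60) = 0.1826 and 0.51/0.1826 = 2.793. Φ(0.833) = 79.8%; noncentral t 79.1%. The first statement is reproduced by the factorial margin with no added assumption.

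**2. Inulin main effect at d = 0.6.** For 60 vs 60, 0.6/0.1826 = 3.286. Φ(1.326) = 90.8%; noncentral t 90.3%.

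**3. 30 vs 30 at d = 0.6.** √(2/30) = 0.2582 and 0.6/0.2582 = 2.324. Φ(0.364) = 64.2%; noncentral t 62.8%. One-sided: Φ(2.324 − 1.645) = 75.1%; noncentral t 74.3%.

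**4. 30 vs 30 at 0.51 SD.** 0.51/0.2582 = 1.975. Φ(0.015) = 50.6%; noncentral t 49.3% (58 df) or 50.0% (115 df).

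**5. Effect of baseline adjustment.** With correlation r, replace d by d/√(1 − r²).

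| Test | r = 0 | r = 0.3 | r = 0.5 |
|---|---|---|---|
| Margin, 0.51 SD | 79% | 83% | 89% |
| One pair, 0.51 SD | 49–50% | 53–54% | 61–62% |
| Margin, d = 0.6 | 90% | 93% | 96% |
| One pair, d = 0.6 | 63% | 68% (115 df) | 76% (115 df) |

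The pair at d = 0.6 reaches 75% at r of about 0.5 and 80% at about 0.57. At those correlations the margin at 0.51 SD would have 89–92%, not 80%.

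**6. Can one test give both figures?** For a given test, the noncentrality is proportional to the effect size, whatever the n, SD or r.

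- 80% power needs 1.960 + 0.842 = 2.802 at 0.51 SD. At 0.6 SD that becomes 2.802 × 0.6/0.51 = 3.296, and Φ(1.336) = 91%. A one-sided test gives 90%.
- In reverse, 75–80% at 0.6 SD means a noncentrality of 2.634–2.802. Multiplied by 0.51/0.6 it is 2.239–2.381, so power at 0.51 SD is 61–66%.

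No single test satisfies both statements.

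**7. Is the inulin margin available from the planned model?** The contrast weights the four adjusted arm means by ±½. Its SE with no baseline gain is √(4 × 0.25/30) = 0.183 SD, the same as for 60 vs 60. A pair has 0.258 SD, and the interaction has √(4/30) = 0.365 SD. With 115 df, the 95% half-widths are 0.36, 0.51 and 0.72 SD.

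**The case against.** The strongest reply has three parts.

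- The plan does not claim that the two statements describe one test. The second is introduced as an addition and changes the group size, and a factorial plan may quote power for both a margin and a cell comparison. That stands. What fails is the label: the second statement calls a 30-per-group comparison a main effect.
- ANCOVA is planned, so a base case with no baseline gain is pessimistic. With a correlation of about 0.5–0.57, a 30-vs-30 pair does reach the stated range. That stands too: the figure is attainable, but for a simple effect and on an assumption that the plan does not give.
- The sample-size text mentions inulin main effects and 60 per arm, and the four-level model yields the margin with full precision. So the gap is one of specification, not feasibility. Even so, neither mention becomes a named contrast in the SAP, while the exercise margin is named.

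A reader might infer more than this, and the documents do not support it.

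- **The study is too small for inulin.** The 0.51-SD claim reproduces for the margin. Read literally as a main effect, the d ≈ 0.6 sentence understates power.
- **The overall four-arm test is a weak inulin test.** It does not isolate inulin at all, and its power depends on the exercise effect. With an inulin effect of 0.51 SD and the difference from the group's previous exercise study (0.84 − 0.2 = 0.64 SD), it has about 97%.
- **The plan must split alpha between the factors or enlarge the sample.** Nothing in the documents requires either.

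**Conclusion.** The point holds as a labelling and specification fault. The d ≈ 0.6 sentence attaches a main effect to a cell-sized group. Its 75–80% matches neither the main effect (about 90%) nor an unadjusted two-sided pair (about 63%). It cannot refer to the same test, on the same assumptions, as the 80% at 0.51 SD, which fits the 60-vs-60 margin.

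The SAP leaves that inulin margin unnamed. If a single inulin pair were used instead, power at 0.51 SD would fall from 79% to about 49–50% with no baseline gain, or from 89% to about 61% at an assumed correlation of 0.5.

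The incompatibility of the two statements does not depend on the correlation, the sidedness or the SD. The individual percentages do depend on the assumptions listed in the working, including 120 participants with complete data.

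**What to change.** - In the SAP, pre-specify the inulin margin for NRS (inulin vs non-inulin, 60 vs 60) as a contrast of the planned baseline-adjusted ANCOVA, alongside the exercise margin.
- State which contrast the primary objective refers to, and reword the objective to match. The inulin margin is the contrast that fits the 0.51-SD claim for supplementation.
- Keep the pairwise comparisons supportive, and report the inulin × exercise interaction with its 95% CI beside the margins.
- Restate the d ≈ 0.6 sentence as either about 90% for 60 vs 60, or about 63% for 30 vs 30 (a simple effect). In both cases give the sidedness and any assumed baseline correlation.

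The cost is wording in the SAP, the objective and the sample-size section; data, model and n = 120 do not change. The downside is that a margin averages over the other factor. It must therefore be read beside an imprecise interaction estimate (95% half-width about 0.72 SD with no baseline gain), and synergy is a stated secondary objective. If the sponsor in fact intends the combination against placebo as primary, the power section has to be rewritten for that contrast.
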